2.2.2 Clinical research

2.2.2.1 Lactin-Vaginal

The first product containing *L. crispatus* CTV-05, Lactin-Vaginal, was under development by The Medicines Company and subject to an IND sponsored by the NIH (BB-IND 6603). In previous clinical studies (three non-IND and two IND) conducted between 1991 and 2000, a total of 304 women received Lactin-Vaginal and were considered evaluable. Although the overall results of the Phase II/III study with Lactin-Vaginal indicated no significant improvement in the cure rate for BV when Lactin-Vaginal was administered with a single 2 gram dose of metronidazole, the

subset of subjects who received Lactin-Vaginal and were colonized with *Lactobacillus crispatus* CTV-05 had a significantly higher clinical cure rate at 30 days than those who were not colonized.

In this Phase II/III study, Lactin-Vaginal was shown to be safe. Adverse events that were reported in the phase II/III study of Lactin-Vaginal (Protocol No. 99-033) were equally distributed between the Lactin-Vaginal and placebo control substance groups, and thus were unlikely related to the *L. crispatus* CTV-05, with the exception of increased vaginal discharge while using the capsules. All 355 women received a single 2 gram oral dose of metronidazole and then were randomized to either Lactin-Vaginal or a control vaginal capsule. Adverse events reported in at least 10% of subjects in this study were abdominal pain, nausea, upper respiratory infections, urinary tract infections, bacterial vaginitis, yeast vaginitis, back pain, urinary frequency, genital pruritus, intermenstrual bleeding, menorrhagia and vaginal discharge. Other less commonly occurring AEs reported included dysuria, urinary urgency, nocturia, dysmenorrhea, vaginal burning and/or pain, genital burning, genital erythema, genital edema, genital lesions, vaginal odor, diarrhea, constipation, dyspareunia, and skin rash. The following Serious Adverse Events were reported in subjects who received Lactin-Vaginal, but all were considered unrelated to treatment: a spontaneous abortion which occurred 69 days after randomization; a ruptured ectopic pregnancy which occurred 79 days after randomization; and a gall bladder removal 92 days after randomization.

Osel, Inc. has acquired the commercialization rights for this product and also the manufacturing facilities used to produce Lactin-Vaginal. Osel, Inc. planned to develop the product for the following indications:

1. To reduce the recurrence rate of BV.

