No serious adverse events were reported in Protocol No. LV-001, and no subject left the protocol due to an adverse event. Long-term safety was assessed by a telephone follow-up at Month 6. Most AEs were mild to moderate. No single severe AE was experienced by more than one subject. Three subjects each experienced a single severe, treatment-related AE: abdominal pain, vaginal candidiasis, vaginal burning sensation, vaginal hemorrhage and vaginal irritation. There were no notable, unexpected AEs, no SAEs and no deaths. No subject left the study due to an AE. The most frequent (≥10%) non-gynecologic AEs reported regardless of causality were abdominal pain NOS (25.0%), headache NOS (23.3%) and diarrhea NOS (10.0%). The most frequent (≥10%) gynecologic AEs reported were vaginal discharge (35.0%), genital pruritis female

(26.7%), vaginal hemorrhage and vaginal odor (15.0%, each), and vaginal burning sensation and vaginal candidiasis (11.7%, each). Forty (88.9%) of subjects participating in this study experienced an AE that was considered by the Investigator to be possibly or probably related to study treatment (LACTIN-V or control capsule). The most common ($\geq 10\%$) non-gynecologic AEs reported as possibly or probably related to study treatment were abdominal pain NOS (22.2%), headache NOS (17.8%) and diarrhea NOS and vaginal candidiasis (11.1%, each). The most common ($\geq 10\%$) gynecologic AEs that were reported by the Investigator as possibly or probably related to study treatment were vaginal discharge (46.7%), genital pruritis female (31.1%), vaginal odour (20.0%), vaginal hemorrhage (17.8%) and vaginal burning sensation (15.6%).

Results obtained indicate that LACTIN-V is safe and well tolerated when administered to healthy subjects once a day for five days at either 5×10^6 cfu/capsule or 5×10^8 cfu/capsule. The safety and vaginal microbiota changes in the placebo control group demonstrated that it was a valid comparison group for use in future studies, instead of using an untreated group.

LACTIN-V Study LV-002

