For Protocol No. LV-003, 111 of 149 subjects (74.5%) reported at least one AE (76.7% of LACTIN-V subjects and 72.4% of placebo control substance subjects). Overall, the most common AEs reported were vaginal discharge (38.9%), vaginitis bacterial NOS (24.2%), genital pruritis female (23.5%) and vaginal odour (22.1%). Adverse events were mostly mild (67.8%) or moderate (28.2%) in severity, and the majority of subjects had AEs that were assessed as possibly or probably related to study product (56.4%). No safety signal was observed for the LACTIN-V group in regard to AEs, with the exception of a higher rate ($\geq 5\%$ difference between treatment groups) of nausea, diarrhea, dysuria, vaginal discharge and vaginal odour. One subject experienced three simultaneous SAEs (hemiparesis, blurred vision in right eye and headache); however, as this subject was in the placebo control substance group, the SAEs were unrelated to LACTIN-V. Two subjects in the LACTIN-V group discontinued study treatment due to AEs; one subject became pregnant and the other reported nausea and diarrhea, which required treatment. No deaths were reported during this study.

LACTIN-V study LV-004

A conducted by Osel Inc. was planned to involve 100 women with a history of recurrent, uncomplicated UTIs who had recently been treated for UTI with a course of antibiotics. Only subjects treated with amoxicillin/clavulanate (Augmentin), a quinolone or nitrofurantoin would have been eligible for enrollment. Subjects were to be randomized to one of two groups (50 subjects per group) to either receive one capsule of LACTIN-V Formulation 1 (at 5×10^8 cfu/capsule) or one placebo daily for five days followed by one capsule per week for 10 weeks. In addition to safety, this study was to evaluate the preliminary efficacy of LACTIN-V in reducing the incidence of symptomatic, probable and asymptomatic UTI. Subjects were to be queried at each clinic visit for urinary symptoms, including dysuria, frequency, urgency, hematuria, flank pain or suprapubic pain. This study was to also evaluate vaginal colonization with lactobacilli, *Lactobacillus crispatus*, strain CTV-05 and *E. coli* following administration of LACTIN-V.

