In late 2007 Osel commenced a small phase I dose-ranging clinical study (LV-005) to assess the safety, tolerability and acceptability of LACTIN -V (Formulation 1) powder delivered with pre-filled vaginal applicators in healthy pre-menopausal women. Study Protocol No. LV-005 also assessed higher doses than used in the prior LV-001 to LV-004 studies; increasing the amount of *L. crispatus* CTV-05 per dose (i.e., per applicator) from 5×10^8 (150 mg) to 1×10^9 (300 mg) and 2×10^9 cfu/dose (600mg). Twelve healthy volunteers were enrolled in 3 blocks of 4 (5×10^8 , 1×10^9 , and 2×10^9 cfu/dose). Each block was randomized in a 3:1 ratio of active product to placebo. Participants used study product for 5 consecutive days, returned for follow-up on days 7 and 14, and had phone interviews on days 2 and 35.

All 12 subjects took 5 doses and completed study follow-up. No SAEs were reported for Study Protocol No. LV-005. All 12 participants took 5 doses and completed study follow-up. Overall, 45 adverse events (AEs) occurred, of which 31 (69%) were genitourinary (GU) AEs. GU AEs appeared evenly distributed between the 3 treatment blocks and between LACTIN-V and placebo arms. The most common GU AEs were vaginal discharge in 5 subjects (42%), abdominal pain in 4 subjects (33%), metrorrhagia in 4 subjects (33%), vulvovaginitis in 4 subjects (33%), vaginal candidiasis in 3 subjects (25%), and vaginal odor in 3 subjects (25%). Forty-one (91%) AEs were mild (grade 1) in severity. All 4 moderate AEs (grade 2) were unrelated to product use. No grade 3 or 4 AEs or serious adverse events (SAE) occurred. Laboratory parameters and colposcopy findings were within normal limits or clinically insignificant. The product was well tolerated and accepted. The study concluded that all 3 dosage levels of LACTIN-V appeared to be safe and acceptable in healthy volunteers. This study was published in 2009 (14).

LACTIN-V study LV-006

Following the phase I clinical study LV-005, Osel, Inc. completed a phase IIa clinical study to further assess the colonization efficiency of *L. crispatus* CTV-05 in otherwise healthy pre-menopausal women diagnosed with BV, administered immediately after completion of a standard antibiotic treatment with metronidazole (MetroGel), using the pre-filled vaginal applicator. In addition, safety, tolerability and acceptability of LACTIN-V (Formulation 1) were assessed.

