At Visit 1, each subject who continues to meet all inclusion and exclusion criteria will be randomized and will receive a box containing 15 applicators. Two extra applicators will be kept at the study site in case a lost or damaged applicator needs to be replaced. The first study applicator will be inserted under supervision in clinic at this visit. The remaining 14 applicators will be inserted daily at bedtime on Days 2–5, and then weekly. Women are to abstain from sexual intercourse and tampon use for 24 hours after each applicator is used. If the subject's partner uses condoms, they will be instructed to use non-spermicidal condoms to avoid killing the *L. crispatus*. The use of other intravaginal products including douching is prohibited throughout the four-month study period. Subjects must agree not to self-medicate with antibiotics or antifungals during the four-month study period. However, subjects may be treated for any on-study vaginal or other infection if a health care provider deems such treatment necessary. Subjects who receive antibiotic or antifungal treatment after commencing the study should continue to insert the study applicator according to their allocated schedule.

Subjects will be provided with a Study Diary to use to record applicator use information during the study. The Study Diary will also be used by subjects to record any symptoms. Subjects will be instructed on how to use these memory aids to remind them to insert the applicator on the designated day and to record the date and time when each applicator was inserted.

Self-reported symptoms will be evaluated at all study visits. Subjects will be queried about the following symptoms:

Nausea or vomiting
Abdominal Discomfort
Diarrhea
Constipation
Rash
Abnormal Vaginal Discharge/Bleeding
Abnormal Vaginal Odor
Genital itching or burning
External genital irritation/swelling
Painful Urination
Urinary Frequency
Urinary Urgency
Blood in urine

Headache
Other: _____

Other: _____

Subjects will be instructed to call the study clinic if they have any unexpected symptoms at any time during the study.

Pelvic examinations will be performed at all visits to evaluate the external genitalia; cervix and vaginal mucosa for signs of irritation at Visits 1 and 6 and if clinically indicated.

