10.10.2 Vaginal Colonization with Lactobacilli

Total lactobacilli (based on culture) will be scored as 1+, 2+, 3+, or 4+.

Colonization with *L. crispatus* strain CTV-05 (based on rep-PCR) will be scored as present or absent (frequency). Number and percent of subjects with positive CTV-05 in each treatment group will be presented. 95% confidence intervals will be calculated to evaluate any difference between the treatment groups.

The differences of these scores between Visit 1 (Day 1, Baseline) and Visits 3 and 6 for each subject will be evaluated within each group and between treatment groups.

10.10.3 *E. coli* Vaginal Colonization

The number (%) subjects with *E. coli* colonization in each treatment group will be summarized by treatment group and visit. 95% confidence intervals will be calculated to evaluate any difference between the treatment groups at a given visit.

10.10.4 Change in Vaginal Microbiota, as assessed by DNA amplification.

The number (%) of specific *Lactobacillus spp.* and uropathogens will be summarized by treatment group and visit. 95% confidence intervals will be calculated to evaluate any difference between the treatment groups at a given visit.

10.10.5 Safety and Tolerability.

The safety endpoints include specific solicited adverse events (AEs), all other reported AEs, serious adverse events (SAEs) and signs of irritation on pelvic examination. The adverse events emerging during the study, their severity and relation to study product will be recorded. Each event will be coded with system organ class and preferred term based on the Medical Dictionary for Regulatory Activities (MedDRA). Number (%) of subjects with AEs will be summarized by system organ class, preferred terms, and treatment group. Severity of AEs and relationship to study product will also be summarized by system organ class, preferred terms, and treatment group. SAEs and reasons for premature termination from study will be summarized by treatment group in frequency and percent. In addition, signs of irritation of the external genitalia, vagina or cervix from pelvic examination, along with their severity and relation to study product will be summarized by treatment group. Furthermore, symptoms and physical findings will be summarized.

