10.10.7 Assessment of Protocol Compliance

Every attempt will be made to select subjects who are eligible and will comply with the protocol. Noncompliant subjects may be discontinued from the study. Protocol deviations will be listed and summarized by treatment arm.

11 RISKS AND DISCOMFORTS TO STUDY SUBJECTS**11.1 LACTIN-V and Placebo Applicator Users****11.1.1 Risks**

The potential risks of LACTIN-V are currently unknown. Pelvic examinations and analyses of vaginal discharge and vaginal microbiota were included in the Phase 1 studies designed to assess LACTIN-V's safety and colonization. The initial Phase 1 safety study of LACTIN-V in healthy women, Protocol LV-001, included colposcopy to evaluate for inflammation or other lesions of the vaginal, cervical or vulvar epithelium. There were no significant differences noted in these safety parameters between treated subjects and those who remained untreated or received the placebo capsule (Osel, Inc., personal communication).

Risks from the administration of LACTIN-V are low since colonization with this type of organism is strongly associated with improved vaginal health. No systemic risks are anticipated, since this is an organism that is applied topically, and thus not absorbed. These risks will be explained in the written informed consent form. Pregnant women, fetuses, prisoners, children, persons with or at risk of STD or women undergoing in vitro fertilization will not be included in this study.

Potential risks to subjects participating in this study include genital or vaginal irritation or symptoms. In the initial Phase 1 study of LACTIN-V (LV-001), the following adverse events were experienced in (at least two) more LACTIN-V treated subjects when the treated groups were compared to the placebo and untreated groups: vaginal discharge, abdominal pain, genital pruritis, vaginal odor, vaginal burning sensation, vaginal candidiasis and diarrhea (Osel, Inc., personal communication). There is also the risk of an allergic reaction to the latex in the condoms provided to subjects who are unaware of their latex allergy and who use these condoms.

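### The solicited symptom list combines abnormal vaginal discharge and vaginal bleeding in one item, so the symptom summary cannot show either one alone

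*Combined protocol and SAP*

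**What the plan says.** Section 5.1 states: "Self-reported symptoms will be evaluated at all study visits". The list that follows puts discharge and bleeding in one line, "Abnormal Vaginal Discharge/Bleeding". Vaginal odor, genital itching or burning, and external irritation or swelling each have a line of their own.

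Section 10.10.5 names solicited adverse events among the safety endpoints, alongside all other reported adverse events. Events are to be coded to MedDRA preferred terms and tabulated by arm. The section closes with a further summary of symptoms and physical findings. Table 1 in Section 10.8 allows Fisher's exact test, optionally, for selected preferred terms, symptoms or findings.

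The protocol's account of earlier studies is as follows.
- **Lactin-Vaginal (2.2.2.1):** adverse events were balanced between groups "with the exception of increased vaginal discharge while using the capsules".
- **LV-003 (2.2.2.2):** the events at least 5 points higher on LACTIN-V were "nausea, diarrhea, dysuria, vaginal discharge and vaginal odour".
- **LV-001 (11.1.1):** the events seen in at least two more treated women were "vaginal discharge, abdominal pain, genital pruritis, vaginal odor, vaginal burning sensation, vaginal candidiasis and diarrhea".
- **LV-005 (2.2.2.2), with the applicator:** "GU AEs appeared evenly distributed between the 3 treatment blocks and between LACTIN-V and placebo arms". LV-006, also with the applicator, is described in similar terms.

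**The concern.** Discharge is on all three lists of events more frequent on product. Bleeding is on none of them. A comparison of the arms on discharge is therefore a natural safety question for this trial, and the list in Section 5.1 is the only place where the text has discharge asked about by name at every visit. A woman who answers yes to the combined item may have had discharge, bleeding or both, and the answer alone does not say which.

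Two things are at stake, both in secondary safety reporting. First, bleeding adds positives to both arms and so dilutes any difference in discharge. Second, a change in bleeding would itself be hidden inside a commoner symptom. The second point matters because in LV-001 vaginal hemorrhage was judged possibly or probably related to study treatment in 17.8% of capsule recipients. The combined item also cannot be set against the product's own earlier safety record, in which the two were counted separately.

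**Working it through.** The plan states no figure for this item, so there is nothing to reproduce. The check has three parts.

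**1. Earlier studies counted the two separately.**
- LV-001, all causes, 60 women: discharge 35.0% = 21/60; vaginal hemorrhage 15.0% = 9/60.
- LV-001, judged possibly or probably related, 45 capsule recipients: discharge 46.7% = 21/45; hemorrhage 17.8% = 8/45.
- LV-005, 12 women: discharge 42% = 5/12; metrorrhagia 33% = 4/12.

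The LV-001 and LV-005 rates pool active and control women. They serve as background rates and do not show a difference between arms.

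**2. Effect of combining the items.** Let d be the risk of discharge in an arm and b the risk of bleeding. Assume b is equal in both arms and independent of d.

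- Combined risk = 1 − (1 − d)(1 − b)
- Difference between arms = (d₁ − d₀)(1 − b)

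Any difference in discharge is therefore multiplied by (1 − b). At b = 15% (LV-001) the factor is 0.85, a loss of 15%. At b = 33% (LV-005) it is 0.67, a loss of 33%.

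**3. Illustrations of power.** The per-arm discharge rates below are assumptions. All tests are two-sided at 0.05. Section 4.3 gives 276 women (138 per arm) and Section 10.4 gives 250 (125 per arm), so both sizes appear.

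| Assumed discharge, control v active | Per arm, method | Asked alone | Combined, b = 15% |
|---|---|---|---|
| 30% v 45% | 138, normal approximation | 15.0 points, power 73% | 40.5% v 53.25%, 12.75 points, power 56.5% |
| 27% v 45% | 125, Fisher's exact | 18.0 points, power 82% | 37.95% v 53.25%, 15.3 points, power 63% |
| 36.4% v 41.4% | 125, Fisher's exact | 5.0 points, power 10% | 45.9% v 50.2%, 4.25 points, power 8% |

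For the first row, bleeding rates of 10% and 33% give combined power of 62% and 39%.

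The third row is the one nearest to a figure in the documents. LV-003 reports discharge in 38.9% overall and a gap of at least 5 points. Placing the minimum gap evenly around 38.9% gives 38.9 ± 2.5, that is 36.4% and 41.4%. At that gap the trial has little power for discharge whether or not the item is split.

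**The case against.** A reader might infer that the trial's safety data cannot report discharge on its own at all. The documents do not support that. Section 7.1.1 requires every adverse event to go on the adverse event page of the case report form, and Section 6.3.5 repeats this for follow-up visits. Sections 7.1.2 and 7.1.3 require severity and causality for each event, which means the investigator has to identify what happened. Section 10.10.5 codes events, and nothing says that the wording of the prompt becomes the event term. If sites record the specific event, discharge can be tabulated from preferred terms. This part of the objection stands. It limits the point to the symptom summary and to a gap in the text: the plan does not say how a positive combined answer becomes an adverse event term.

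There are other routes too. Women are asked about adverse events at all visits (4.4.2) and about symptoms with applicator use at Visits 2–6 (6.9.3). They also grade symptoms in the diary for the first 7 days (Appendix B). As described, none of these asks about discharge by name, and the diary grading ends while weekly dosing continues. The diary page (Appendix C) and the case report forms are not in the text reviewed and may already separate the two symptoms.

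Two further readings go too far. One is that discharge is the main established effect of this product. Section 2.2.2.1 singles it out only for the older Lactin-Vaginal capsule. It is one of five events in LV-003 and one of seven in LV-001, and the applicator studies describe balanced adverse events, though in only 12 and 24 women. The other is that bleeding is unrelated background noise, which the 17.8% in LV-001 contradicts.

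Finally, no powered safety comparison is planned, so a loss of power breaks no commitment in the plan.

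**Conclusion.** The point holds for the solicited item. As the list is printed, the symptom summary cannot show discharge or bleeding alone, and merged answers cannot be separated after collection. Under equal and independent bleeding, the difference in discharge shrinks by about 15% at the LV-001 bleeding rate and by about a third at the LV-005 rate, which rests on 12 women. If bleeding differs between arms or goes together with discharge, the size of the distortion changes, and if bleeding differs its direction may change too.

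The consequence for detecting an effect depends on per-arm rates that the documents do not give. It ranges from a drop of some 17 to 19 points of power in the larger assumed effects to about 2 points at the LV-003 minimum gap. The primary endpoint, sample size and type I error are untouched. Discharge may still be reported from coded adverse event terms. The priority is minor: a cheap improvement to secondary safety reporting that has to be made before data are collected.

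**What to change.** In Section 5.1, replace the combined line with two: *Abnormal vaginal discharge* and *Abnormal vaginal bleeding*. Make the same change on any case report form or diary page that uses this list; where a page already separates the two, only Section 5.1 needs to follow it. In Section 10.10.5, summarise each symptom by arm with the risk difference and 95% confidence interval.

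If the list cannot be changed, the least that would help is a sentence requiring the site to record which symptom was present whenever the combined item is positive.

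The cost is one extra tick box and one extra table row, with no added visit, procedure or staff.
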